4.8.2 Effectiveness Outcomes

The **primary effectiveness outcome** is:

1. **Oral antibiotic treatment failure**, defined as a change in antibiotic (change in class of oral antibiotic or step up to intravenous therapy) within 7 days due to worsening infection, which is defined as:
 - a. New fever (temperature $\geq 38.0^{\circ}\text{C}$) or *persistent* fever at Day 3 follow up; or
 - b. Increasing area of erythema $\geq 20\%$ from baseline; or
 - c. Increasing pain ≥ 2 points from baseline (numeric rating scale)

The secondary effectiveness outcomes are:

2. Clinical cure (no erythema, pain and fever) at day 7
3. Clinical response ($\geq 20\%$ reduction in area of erythema compared to baseline) at day 3
4. Adverse events (e.g. vomiting, diarrhea, rash) at 14-day telephone follow-up
5. Unplanned i) return ED visits; and ii) hospitalization at 14-day telephone follow-up

Baseline clinical data will be recorded at the index ED visit. Patients will be assessed at a home visit by the research assistant on: 1) Day 3 (mid-therapy); and 2) Day 7 (end-of-therapy). If criteria are met for worsening infection, they will be sent to the ED for evaluation. If a home visit is not possible, the following alternate methods of follow up will be offered to patients:

1. Video follow up via a mobile device (tablet or phone) using FaceTime, Zoom or Skype. The patient must own a mobile device with one of these applications in order to proceed with this option. If this option is chosen, the patient will be given a disposable tape measure and disposable temperature strip so that they can measure the dimensions of erythema and temperature, respectively during the video follow up. The patient will be asked to download a free mobile application (Preventicus Heartbeats; <https://www.preventicus.com/en/>) that will allow the patient to measure their heart rate at the time of follow up.
2. Return to the ED for assessment. In this case, hospital parking fees will be reimbursed for the patient

Study participants will complete a questionnaire on Day 7 regarding effectiveness of blinding, medication adherence and adverse events.

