4.12 Data Analysis

Baseline demographic and clinical characteristics of participants will be described using descriptive statistics. Primary and secondary feasibility outcomes will be described using frequency and proportion with two-side 90% confidence intervals. Primary and secondary effectiveness outcomes will be described using frequency and proportion in each arm, together with 95% confidence intervals for the difference between the two arms. Analysis will proceed according to an intention-to-treat protocol.

While every effort will be made to avoid attrition, the prevalence of any missing data will be described in each arm and multivariable regression analysis will be used to identify baseline characteristics associated with attrition. Any identified characteristics will need to be adjusted for in the primary and secondary outcome analyses to avoid bias due to attrition. Single or multiple imputation will be used as sensitivity analysis to explore the implications of non-randomly missing data under extreme assumptions about attrition.

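### Day 3 erythema area is measured but planned for analysis only as a 20% responder proportion; a baseline-adjusted analysis that tolerates zero areas would add precision at little cost

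*Combined protocol and SAP*

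**What the plan says.** All references are to the combined protocol and SAP.

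- **Outcome.** In section 4.8.2, Day 3 clinical response is a 20% or greater "reduction in area of erythema compared to baseline) at day 3". The area is used in one other place, also as a yes/no item: "Increasing area of erythema" by at least 20% is one of the criteria for worsening infection in the primary effectiveness outcome.
- **Measurement.** Both definitions need a numeric area at baseline and at follow-up. Section 4.8.2 states that "Baseline clinical data will be recorded at the index ED visit". For the video option it supplies a tape measure "so that they can measure the dimensions of erythema and temperature, respectively during the video follow up".
- **Analysis.** Section 4.12 reads: "Primary and secondary effectiveness outcomes will be described using frequency and proportion in each arm". The comparison of arms rests on these figures "together with 95% confidence intervals for the difference between the two arms". The section states no hypothesis test and no analysis of area on a continuous or ordinal scale.
- **Adjustment.** Section 4.12 has one provision, for baseline characteristics found to be associated with attrition: "Any identified characteristics will need to be adjusted for in the primary and secondary outcome analyses to avoid bias due to attrition". Neither baseline area nor cellulitis location, the stratification factor in section 4.7, is named.
- **Size and purpose.** Section 4.11 sets 64 patients from the recruitment rate. Section 3 gives preliminary evidence of effectiveness as the second of two specific goals.

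**The concern.** A 21% reduction and a 90% reduction count as the same result, and a 19% reduction counts as the opposite one. With about 32 patients per arm, the responder difference will be imprecise whatever happens. Because recruitment alone sets the sample size, extra precision on early response can come only from the analysis. Baseline area enters only as the denominator of the percentage change. It is not used as a covariate to remove variation between patients.

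What is at stake is how much the pilot can say about the dose effect on early response, using measurements it must take anyway.

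**Working it through.** **1. The plan's own figure.** Section 4.11 assumes 35% recruitment of 180 approached: 0.35 × 180 = 63, close to the target of 64. The exact (Clopper-Pearson) 90% interval for 63/180 is 0.2909 to 0.4128, which matches the stated 0.291 to 0.413. No Day 3 response figure enters this, and the documents give none to reproduce.

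**2. Precision of the planned comparison.** Inputs: 64 patients randomised 1:1, so 32 per arm; the response rate p is assumed. The 95% half-width is 1.96 × √(2p(1−p)/32).
- p = 0.5: 1.96 × 0.125 = 0.245
- p = 0.8: 1.96 × 0.100 = 0.196

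**3. Information lost by the cut.** Assume that log change in area is normal and the effect is small. The efficiency of the cut against a continuous analysis of the same change is φ(z_p)² / [p(1−p)].

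| Responder rate (assumed) | Efficiency | Loss | Equivalent of 64 patients |
|---|---|---|---|
| 50% | 0.3989²/0.25 = 0.637 | 36% | 41 |
| 70% | 0.3477²/0.21 = 0.576 | 42% | 37 |
| 80% | 0.2800²/0.16 = 0.490 | 51% | 31 |
| 90% | 0.1755²/0.09 = 0.342 | 66% | 22 |

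**4. Against a baseline-adjusted analysis.** If baseline has correlation ρ with the change, multiply the efficiency by (1−ρ²). For assumed ρ of 0.3 to 0.5 the loss is 42–52% at a 50% responder rate, 55–63% at 80% and 69–74% at 90%.

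**5. Worked example, no zero areas.** Assumptions: SD of log area 0.8, baseline to Day 3 correlation 0.6, control median area 0.8 of baseline, geometric mean ratio 0.66.
- SD of log change: 0.8 × √(2 × 0.4) = 0.716. Control responders: 50%. High-dose responders: Φ(0.416/0.716) = Φ(0.58) = 72%.
- Cut: 0.22 / √(0.25/32 + 0.2016/32) = 0.22/0.119 = 1.85 standard errors.
- Log-area ANCOVA: residual SD 0.8 × √(1−0.36) = 0.64; standard error 0.64 × √(2/32) = 0.16; 0.416/0.16 = 2.60 standard errors.
- Efficiency: (1.85/2.60)² = 0.51. Step 4 agrees: ρ² = (1−0.6)/2 = 0.20, and 0.637 × 0.80 = 0.51.
- Simulated power is about 0.46 for the cut and 0.71 for the ANCOVA. The plan proposes no test, so power serves here only as a measure of precision.

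**6. The same example with zero areas at Day 3.** A log of zero is undefined, so zeros were replaced by a small value (1% of median baseline area, an assumption). Zeros fell at random.

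| Zero areas | Cut | Log-area ANCOVA | Rank-based ANCOVA |
|---|---|---|---|
| 5% | 0.45 | 0.33 | 0.55 |
| 10% | 0.39 | 0.20 | 0.43 |

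At about 20% zeros the rank-based analysis also falls below the cut.

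**7. Heavy tails.** With t errors on 3 degrees of freedom, the simulated loss of the cut against the change score ranged from 9% to 76%. Against ordinary ANCOVA, the efficiency of the cut ranged from 0.42 to about 1.07, so the gain can disappear.

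**The case against.** The strongest case against the point is that it concerns a secondary outcome, described rather than tested, in a trial whose primary outcome is recruitment. No decision in the pilot turns on Day 3 response. A 20% reduction is easy to read and mirrors the 20% increase in the failure definition. Percentage change already uses the baseline value, and section 4.12 does allow some covariate adjustment. The obvious alternative, log-area ANCOVA, breaks down when some patients have no erythema left at Day 3, which the responder cut handles without any substitution.

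Much of this stands. It limits the weight of the point and rules out replacing the responder proportion or relying on log area alone. It does not remove the point: the plan commits to between-arm intervals as preliminary evidence, and a rank-based or ordinal analysis of the same data handles zeros and is usually more precise.

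A reader might also infer that the pilot's data would improve the sizing of the full trial. Appendix A does not support this. It sizes that trial on binary treatment failure (20%, a difference of 5%, 2552 participants), and neither an SD nor a correlation of erythema area enters that calculation.

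**Conclusion.** The point holds as a modest, inexpensive improvement. Day 3 area is planned for analysis only as a responder proportion, with no analysis of the area itself and no prespecified adjustment for baseline area or location.

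The size depends on assumptions. Under a normal model for log change the loss is about 36% at a 50% responder rate and about 66% at 90%, and more against a baseline-adjusted analysis. It may be much smaller with heavy-tailed areas or many zeros.

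Two stronger readings are tempting, and the documents support neither:
- **A fixed loss of 40–60%.** Against the same change score this needs responder rates of about 66% to 87% and normality. The documents give neither.
- **A wholly unadjusted analysis.** Section 4.12 adjusts for characteristics linked to attrition. What is missing is prespecified adjustment for baseline area and location.

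This is a matter of precision. The planned responder comparison remains valid.

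**What to change.** 1. Keep the 20% responder proportion and its 95% confidence interval as the stated secondary outcome.
2. In section 4.12, prespecify beside it a baseline-adjusted analysis of Day 3 area on arm, baseline area and cellulitis location. Use a rank-based ANCOVA or an ordinal model, with zero areas placed at the best rank.
3. Report a log-area ANCOVA, as a ratio of geometric means with a 95% confidence interval, only if no or almost no Day 3 areas are zero. Set that threshold before unblinding.
4. State how areas measured after a change of antibiotic are used. The plan gives no such rule for Day 3 response, and the two analyses should handle these patients consistently.

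The cost is a few lines of analysis plan and a little programming, with no new measurements or visits. The added effect measure is less directly readable than a response rate, which is still reported.

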1. INTRODUCTION

Background

Uncomplicated, non-purulent cellulitis is an infection describing the subcutaneous tissue of the skin.¹ Group A streptococcus (*Streptococcus pyogenes*), β -hemolytic streptococci and methicillin-susceptible *Staphylococcus aureus* are the most common causative agents for non-purulent cellulitis. Patients typically present to the emergency department (ED) with pain, redness, swelling and induration of the affected skin. The borders of the reddened affected skin are irregular and patchy in patients with cellulitis. A minority of patients may exhibit signs of systemic illness, such as fever or tachycardia. The diagnosis of non-purulent cellulitis is clinical. Once the diagnosis is made, emergency physicians are expected to select appropriate antibiotic therapy. The physician must select the appropriate route (oral versus intravenous), agent, dose frequency and duration.

Burden of Disease

Cellulitis is a common condition diagnosed and managed in the ED and carries significant financial burden on healthcare systems globally. Extrapolating from US data², there are approximately 193,000 Canadian ED visits per year for cellulitis. Although Canadian data are lacking, a single Vancouver ED diagnosed 2234 patients with skin and soft tissue infections from 2003 to 2004, representing 2% of all ED visits.³ A 2011 report by the Canadian Institute for Health Information found that cellulitis was the 5th most common reason for an ED visit in patients aged 45 to 64 years.⁴ Cellulitis is responsible for a significant healthcare system burden due to hospital admission and subsequent costs. We conducted a health records review at The Ottawa Hospital Civic and General campuses, and found that 29.6% of all ED patients with non-purulent cellulitis are admitted to hospital.⁵ A study in the United States reported an average cost of \$8023 USD for hospitalized patients with skin and soft tissue infections with a mean length of stay of 4.9 days.⁶

Current Guidelines

Owing to a lack of high-quality evidence, published empiric treatment guidelines are largely based on expert opinion.⁷⁻¹⁰ There are currently no Canadian guidelines for the management of skin and soft tissue infections. Despite the increasing burden of this common presentation, current evidence is lacking regarding the optimal management of cellulitis.

Oral Antibiotic Therapy: Cephalexin

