4.9 Data Collection

Data will be collected by the research assistant at the index ED visit, and on follow-up visits (day 3, 7 and 14). Any paper files with identifying information will be kept separately and securely from all other study sites. These files will be kept in a locked filing cabinet in a locked office in an OHRI research office on F6 (Civic campus of The Ottawa Hospital). Data will be extracted from each record of treatment, which includes physician, nursing, consultant, triage, ambulance, and any consultation reports. This information will be obtained from hospital medical records (i.e. EPIC). Data will be entered into a secure web-based electronic data capture system. No identifying personal health information will be recorded into this system. Any potentially identifying information in the case record forms for each assessment plus the day 7 patient questionnaire are uploaded separately in the OHSN-REB application.

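### Under the fallback video option the patient measures the erythema, but the 20% change criteria compare that reading with a research assistant's baseline, with no common measuring procedure written down

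*Combined protocol and SAP*

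**What the plan says.** All of the following is in the protocol; section 4.8.2 is the source unless another is named.

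- **Criteria.** One of three alternative signs of worsening infection is "Increasing area of erythema $\geq 20\%$ from baseline". Day-3 clinical response is the mirror image, a fall of at least 20% in erythema area from baseline.
- **Baseline.** "Baseline clinical data will be recorded at the index ED visit". Section 4.9 names the collector: "Data will be collected by the research assistant at the index ED visit, and on follow-up visits (day 3, 7 and 14").
- **Default follow-up.** "Patients will be assessed at a home visit by the research assistant on: 1) Day 3 (mid-therapy); and 2) Day 7 (end-of-therapy").
- **Fallback.** If a home visit is not possible, the patient may be seen by video or return to the ED. By video, "the patient will be given a disposable tape measure and disposable temperature strip so that they can measure the dimensions of erythema and temperature", and this is done during the call.
- **Consequence of worsening.** "If criteria are met for worsening infection, they will be sent to the ED for evaluation".
- **Primary effectiveness outcome.** Treatment failure is "defined as a change in antibiotic (change in class of oral antibiotic or step up to intravenous therapy) within 7 days due to worsening infection".
- **Nature of the lesion.** Section 1 (Background) says: "The borders of the reddened affected skin are irregular and patchy in patients with cellulitis".

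The protocol text gives no rule for turning dimensions into an area, no marking of the border or of the measured axes, no description of the research assistant's part in the video measurement, and no analysis by follow-up mode.

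**The concern.** Both erythema criteria are ratios. At a home visit the research assistant supplies the follow-up reading as well as the baseline, so any habit in where the edge is placed tends to cancel. By video the baseline is the research assistant's and the follow-up reading is the patient's, so a systematic difference between the two goes straight into the ratio. With an irregular, patchy border, where the edge lies is a judgement, and a difference of that kind is plausible.

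Area also magnifies small linear differences, so a modest shift can cross the 20% line when nothing has changed clinically. At stake for video patients are a wrong day-3 response, an ED referral without true spread, or true spread that goes unflagged on this criterion. The pilot is meant to test and refine procedures (section 2), so a measuring method that varies with follow-up mode is best settled here, before the multicentre trial.

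**Working it through.** **Inputs from the documents.** Area ratio of at least 1.20 for worsening and at most 0.80 for response (section 4.8.2); target of 64 patients (section 4.11); 20% failure on standard dose (Appendix A).

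**Inputs that are assumptions.** Area proportional to length × width (a rectangle and an ellipse give the same ratio); independent reading error with an SD of 5–10% per dimension on each occasion; a patient-versus-assistant shift of 5% per dimension, in either direction. The documents give none of these. There is no stated figure in the plan to reproduce.

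**Step 1: linear thresholds, lesion truly unchanged, same relative error e in both dimensions.** The area ratio is (1 + e)².

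- Worsening: e = √1.20 − 1 = 1.0954 − 1 = 9.5%.
- Response: e = 1 − √0.80 = 1 − 0.8944 = 10.6%.
- Example: 10 × 10 cm read as 11 × 11 cm is 121 against 100 cm², or +21%, which meets worsening. Read as 8.9 × 8.9 cm it is 79.2 cm², or −21%, which meets response.

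**Step 2: when a 10% error does not cross a threshold.**

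| Situation | Apparent change | Threshold met? |
|---|---|---|
| +10% in one dimension only | +10% | No |
| +10% in one, −10% in the other | 1.1 × 0.9 − 1 = −1% | No |
| +10% in both, true area down 10% | 1.21 × 0.90 − 1 = +8.9% | No |
| −10% in both | 0.81 − 1 = −19% | No (just short of response) |

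**Step 3: chance of crossing at one visit with no true change.** The log area ratio sums four independent errors (two dimensions, two occasions), so its SD is √4 = 2 times the per-dimension SD: 0.10 or 0.20. Its mean is 0 with no shift, 2 ln 1.05 = +0.098 if the patient reads 5% longer, and 2 ln 0.95 = −0.103 if 5% shorter. The thresholds are ln 1.20 = 0.182 and ln 0.80 = −0.223. With Φ the standard normal distribution function,

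P(worsening) = 1 − Φ((0.182 − mean)/SD) and P(response) = Φ((−0.223 − mean)/SD).

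| Shift per dimension | False worsening, error SD 5% / 10% | False response, error SD 5% / 10% |
|---|---|---|
| None | 3.4% / 18.1% | 1.3% / 13.2% |
| Patient 5% longer | 19.8% / 33.6% | 0.1% / 5.4% |
| Patient 5% shorter | 0.2% / 7.7% | 11.4% / 27.3% |

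For example, the first entry of the second row is 1 − Φ((0.182 − 0.098)/0.10) = 1 − Φ(0.85) = 19.8%.

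**Step 4: what belongs to the video option.** The first row applies equally to a research assistant who measures twice. Only the difference from that row comes from the change of rater: for false worsening, about +16 points (3.4% to 19.8%, or 18.1% to 33.6%) for longer readings, and −3 to −10 points for shorter ones.

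**Step 5: missed spread.** A true increase of 30%, read 5% short in each dimension, gives 1.30 × 0.95² = 1.17, below 1.20. Criterion (b) is then not met.

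**The case against.** The strongest reply has five parts.

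- **Treatment failure is protected.** A reader might infer that tape error feeds directly into the primary effectiveness outcome. The documents do not support that: a patient who meets a worsening criterion is first evaluated in the ED, and failure needs an actual antibiotic change. This stands. The protection does not extend to day-3 response, which has no such filter, or to a falsely low reading, which triggers no referral under criterion (b). Fever and pain can still flag such a patient.
- **The measurement is live.** The patient measures during the call, and section 4.9 has the research assistant collecting follow-up data, so this is not unsupervised self-report. That is fair, but no guiding procedure is written, and instructions in the separately uploaded case record forms cannot be judged from here.
- **A 10% reading difference is not enough by itself.** A reader might also infer that any 10% discrepancy triggers worsening. It must be over-reading, in both dimensions, of a lesion that has not shrunk (step 2).
- **Much of the error is not specific to video, and the shift may go either way.** Both are correct; hence the no-shift row and the two directions in step 3.
- **The weight in this pilot is small.** Video is a fallback whose share is not stated. With 32 patients per arm and 20% failure in each, the 95% interval for the difference has a half-width of about 1.96 × √(2 × 0.20 × 0.80/32) = 0.196, or 20 points, so imprecision dominates. The full-trial sample size in Appendix A does not use pilot erythema data. This limits the consequence, but a pilot is the right place to settle a procedure that is cheap to standardise.

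Nor do the documents support reading this as bias in favour of one dose. Patients, treating physicians and the research team are blinded (section 4.7), so the error should be roughly equal in both arms.

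**Conclusion.** The point holds as a measurement weakness of limited reach. In video patients the person who measures differs between baseline and follow-up, and the protocol text does nothing to hold the method constant. An over-reading of about 9.5% in both dimensions, or an under-reading of about 10.6%, is enough to cross a 20% criterion on an unchanged lesion. A 5% shift between raters would move false worsening from 3–18% to 20–34%, or down to about 0.2–8%, depending on its direction.

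These rates rest on length × width as area, on the assumed error SDs and shift, and on no true change. They apply only to visits done by video and cannot be scaled to the whole trial, because the video share is unknown. The outcomes directly exposed are day-3 clinical response and referral to the ED. Any effect on the treatment-failure rate is indirect, and the comparison between arms is more likely diluted than biased.

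**What to change.** In section 4.8.2, state the following.

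1. At the index visit the research assistant marks the erythema edge and the ends of the two measured axes with a skin marker, for every patient, because video users are not known in advance.
2. All follow-up measurements, including video, are taken along those axes. On video the research assistant directs the placement of the tape and reads it on screen.
3. Area is computed from the two dimensions by one stated formula.
4. The follow-up mode at each assessment is recorded on the case record form. Erythema-based outcomes are reported by mode as a descriptive sensitivity analysis, with a note that mode is determined after randomisation, so differences between modes are not a randomised comparison.

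A separate baseline reading by the patient is not recommended. It would be needed for nearly everyone, and it would put two kinds of baseline inside one outcome.

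The cost is a skin marker, a few minutes of research assistant time at the index visit, and one form field. No visit or staff is added, and no treatment or referral rule changes.
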